## **2.6. Good Clinical Practice and Regulatory Requirements**

This study will be conducted in accordance with the guidelines of Good Clinical Practice (GCP) and the applicable regulatory requirement(s), including the archiving of essential documents. Detailed information regarding study conduct is found in [Sections 10, 11, 12, and 13](#).

## **2.7. Population to be Studied**

Non-ambulatory adolescents and adults with DMD will be enrolled in this trial. A detailed inclusion/exclusion list is provided in [Section 5](#).

### **3. OBJECTIVES**

#### **3.1. Primary Objective**

The primary objective of this trial is to estimate pamrevlumab's efficacy in non- ambulatory subjects with DMD.

#### **3.2. Secondary Objectives**

The following are the secondary objectives of this trial:

1. To evaluate safety and tolerability of pamrevlumab administered intravenously every 2 weeks
2. To assess pharmacokinetics of pamrevlumab in the targeted pediatric population
3. To evaluate pharmacodynamic markers of pamrevlumab's effects in DMD

## 4. STUDY DESIGN

### 4.1. Endpoints and Assessments

#### 4.1.1. Primary Endpoint

The primary endpoint is the annual change from baseline to Week 104 in percent predicted forced vital capacity (FVC) during treatment with pamrevlumab.

#### 4.1.2. Secondary Endpoints

The following are the secondary endpoints:

- Change from baseline to Week 104 in forced expiratory volume (FEV1), maximum inspiratory pressure (MIP), maximum expiratory pressure (MEP), peak expiratory flow (PEF), peak cough flow
- Change in LVEF from baseline to Week 104
- Change from baseline to Week 104 in Performance of Upper Limb (PUL) Score
- Change from baseline to Week 104 in grip strength, pinch strength, and Brooke scale for upper extremity
- Change from baseline to Week 104 in cardiac fibrosis score assessed by MRI
- Change from baseline to Week 104 in upper arm (bicep) muscle fat and fibrosis assessed by MRI

#### 4.1.3. Exploratory, Pharmacokinetic and Pharmacodynamic Outcome Measures

Exploratory outcome measures for this trial are:

- Pharmacokinetic (PK) profile of pamrevlumab (including Cmin, Cmax, AUCtau, and t1/2) [In the first 12 subjects to have PK/PD samples though Day 14]
  - In the overall population
  - In subjects 12 to 16 years of age, inclusive
  - In subjects older than 16 years
  - Comparison of PK profiles across age groups
- Plasma and urine CTGF
- Creatine kinase (CK)
- Circulating biomarkers
- Exploratory analyses on primary and secondary efficacy endpoints at week 156 will be conducted at the end of the study.

#### **4.1.4. Safety Assessments**

Adverse events (AEs), serious adverse events (SAEs), clinical laboratory tests and discontinuation of treatment for treatment-related AEs serve as the safety assessments for this trial.

#### **4.2. Trial Overview**

This study will be an open-label, single arm study that will initially enroll approximately 22 subjects and includes an open label extension (OLE). Each subject will receive pamrevlumab (35 mg/kg, every 2 weeks) for a minimum of 104 weeks and will transition onto the OLE within 2-3 infusions from the approval of the amendment. An interim analysis will be conducted after at least 10 to 12 subjects have completed 1 year of treatment. As a result, sample size may be readjusted to a total of approximately 32 subjects.

All subjects will be closely monitored for safety (including trends of pulmonary function tests: FVC, mean inspiratory flow, and peak expiratory flow) on a continuous basis.

Upon completion of treatment or premature discontinuation from the trial, subjects will be asked to return to the investigative site to complete final safety and efficacy assessments.

#### **4.3. Study Treatment**

##### **4.3.1. Dose and Schedule**

Each subject will receive pamrevlumab (35 mg/kg) intravenously every 2 weeks (q2w). See [Section 6](#) for detailed information on study drug formulation, storage, and administration.

##### **4.3.2. Rationale for Dose and Schedule**

The pamrevlumab dose is based on results of a study in adult subjects with pancreatic cancer. In that study ([Section 2.3.4.1](#)), minimum pamrevlumab blood levels (Cmin)

$\geq 150$  mcg/mL were associated with increased median survival and 1 year survival compared to subjects with Cmin  $< 150$  mcg/mL. Given the apparent threshold effect for increased benefit when minimal pamrevlumab exposure is  $\geq 150$  mcg/mL and based on PK analysis using these data, the planned dose of 35 mg/kg administered every 2 weeks is projected to achieve this minimum exposure in the targeted DMD study population.

#### **4.4. Concomitant Medications, Procedures and Nondrug Therapies**

Subjects will receive full supportive care as required by their clinical condition. Management of corticosteroid dose is up to the discretion of the physician. All subjects should be monitored for osteoporosis in accordance with the respective institutional standard of care for DMD patients receiving glucocorticoid therapy.

Investigational agents, and those that receive marketing authorization during this trial, or approved product for DMD (e.g. eteplirsen) are prohibited. Use of deflazacort if regarded by the principal investigator as standard of care is allowed.

Concomitant medications (any prescription and/or over-the-counter [OTC] preparation) and procedures or nondrug therapies (e.g., physical therapy or acupuncture) used by a subject while

participating in this clinical trial must be recorded from the Screening Visit through the End-of-Study Visit.

Questions regarding potential impact of concomitant medications on evaluability of subjects should be addressed to the attention of the FibroGen Medical Monitor.

#### **4.4.1. Contraception**

Subjects with female partners of childbearing potential are required to use two forms of contraception during the conduct of the study and for 3 months after the last dose of study drug.

Pregnancy, spontaneous or therapeutic abortion, or events related to pregnancy of a partner must be reported ([Section 8.3.6](#)).

#### **4.5. Safety Plan**

An ongoing safety review is facilitated by the unblinded nature of the study. FibroGen will review safety data and will communicate the results of these reviews to investigators by email or teleconference on a regular basis. In addition, FibroGen will review safety experience with investigators during teleconferences that will be held at least quarterly and include the conclusions of the Data Monitoring Committee's (DMC) latest data review.

FibroGen will notify investigators immediately if a new safety risk is identified.

#### **4.6. Data Monitoring Committee**

A DMC will be utilized and will be composed of external experts. Composition and responsibilities of the DMC are defined in a separate DMC charter.

DMC responsibilities include review of safety data, and may include available pharmacokinetic data, and pulmonary function tests.

## 5. STUDY ENROLLMENT AND WITHDRAWAL

### 5.1. Inclusion Criteria

Subjects must meet all of the following criteria in order to be eligible for the study:

1. At least 12 years of age
2. Written consent/assent by patient and/or legal guardian as per regional and/or IRB requirements
3. Non-ambulatory
4. Brooke Score for Arms and Shoulders  $\leq 5$
5. Diagnosis of DMD by medical history and confirmed Duchenne mutation in available genetic testing using a validated genetic test
6. Able to perform spirometry
7. Able to undergo cardiac and extremity (upper arm) MRI
8. Percent predicted FVC between 40 and 90, inclusive
9. At least one historical FVC % predicted value within 18 months of baseline
10. Left ventricular ejection fraction  $\geq 45\%$  as determined by cardiac MRI at screening or within 3 months prior to Day 0
11. Subjects currently receiving heart failure cardiac medications (e.g. angiotensin converting enzyme inhibitors, angiotensin-receptor blockers, and beta-blockers) must achieve a stable regimen for at least 3 months prior to screening
12. On a stable dose of corticosteroids for a minimum of 6 months prior to screening with no substantial change in dosage for a minimum of 3 months (except for adjustments for changes in body weight) prior to screening and no foreseen change in corticosteroid use during the course of study participation
13. Received pneumococcal vaccine and is receiving annual influenza vaccinations
14. Adequate renal function: cystatin C  $\leq 1.4$  mg/L
15. Adequate hematological function:
  - a. Platelets  $>100,000/\text{mcL}$
  - b. Hemoglobin  $>12\text{ g/dL}$
  - c. Absolute neutrophil count  $>1500/\mu\text{L}$
16. Adequate hepatic function:
  - a. No history or evidence of liver disease
  - b. gamma glutamyl transferase (GGT)  $\leq 3 \times$  upper limit of normal (ULN)
  - c. Total bilirubin  $\leq 1.5 \times \text{ULN}$
17. If sexually active, will use medically accepted contraceptives during participation in the study and for 3 months after the last dose of study drug

## 5.2. Exclusion Criteria

Subjects must not meet any of the following criteria in order to be eligible:

1. Requires  $\geq 16$  hours continuous ventilation
2. Prior or ongoing medical condition that in the investigator's opinion, could adversely affect the safety of the subject, makes it unlikely that the course of 156 weeks of treatment and follow-up would be completed, or could impair the assessment of study results
3. Anticipated spine surgery within 156 weeks
4. Severe uncontrolled heart disease including any of the following:
  - a. Need for intravenous diuretics or inotropic support within 3 months prior to screening
  - b. Hospitalization for a heart failure exacerbation or arrhythmia in last 3 months
5. Arrhythmia requiring anti-arrhythmic therapy
6. Hospitalization due to respiratory failure in the last 6 weeks
7. Poorly controlled asthma or underlying lung disease such as bronchopulmonary dysplasia
8. Known or suspected active hepatitis B or C or history of HIV
9. BMI  $\geq 40$  kg/m^2 or weight  $> 117$  kg
10. Exposure to another investigational drug or another approved product for DMD (e.g. eteplirsen) within 28 days prior to start of study treatment (or 5 half-lives of the product whichever is longer) prior to first screening visit with the exception of deflazacort. Use of deflazacort if regarded by the principal investigator as standard of care is allowed.

## 5.3. Subject Withdrawal

Subjects may withdraw from the study at any time.

The investigator may remove a subject from study treatment for the following reasons:

- Adverse events, which in the opinion of the Principal Investigator and/or FibroGen preclude further study drug dosing
- Nonadherence to protocol-defined procedures, in particular missing of 3 or more sequential study drug infusions
- Not available for safety assessments

Subjects who discontinue the study early should be strongly encouraged to complete the evaluations described in [Section 7.1.3](#).

## 5.4. Replacement of Subjects

Subjects may be replaced in this study if a subject's participation is not terminated due to safety or tolerability issues and is replaced prior to completion of targeted recruitment into the study. Replacement decisions will be made between the sponsor and investigator on a case-by-case basis.

## **5.5. Study Termination**

This trial can be terminated by the sponsor at any time for any reason.

## 6. STUDY DRUG/TREATMENT SUPPLY

### 6.1. FibroGen Investigational Product

Pamrevlumab is a fully human IgG1 kappa monoclonal antibody that binds to CTGF.

#### 6.1.1. Formulation

Pamrevlumab is supplied in single-use glass vials containing 10 mL or 50 mL of a sterile, preservative-free solution (100 mg pamrevlumab/vial or 500 mg pamrevlumab/vial respectively). The solution is composed of 10 mg/mL pamrevlumab, 1.60 mg/mL l-histidine, 3.08 mg/mL l-histidine HCl, 8.01 mg/mL sodium chloride and 0.05 mg/mL polysorbate 20, resulting in a solution with a tonicity of approximately 290 mmol/kg and a pH of 6.0. If different vial sizes or new formulations are introduced during the course of the study, updates to formulation, storage, etc. will be provided through an amendment to the Pharmacy Manual and investigative site staff training.

#### 6.1.2. Study Drug Packaging and Labeling

Labels will be prepared and will comply with Good Manufacturing Practice and USA regulatory guidelines.

#### 6.1.3. Storage

Vials of pamrevlumab must be stored refrigerated (2°C to 8°C), in a temperature- controlled and monitored environment, protected from light, and in a securely locked area to which access is limited to appropriate study personnel. Documentation of the storage conditions must be maintained by the site for the entire period of study participation.

#### 6.1.4. Preparation of Dose for Administration

The dose of pamrevlumab (35 mg/kg) for the first infusion should be based on body weight obtained during screening. Dose will be adjusted based on body weight taken every 3 months thereafter. Pamrevlumab may be administered undiluted or, for convenience of infusion, may be diluted with 0.9% Sodium Chloride Injection according to the Dose Preparation Instructions in the Study Reference Investigational Product (IP) Manual.

Pamrevlumab will be administered as soon as possible after release from the site's pharmacy and within 48 hours of preparation and within 6 hours if left at room temperature after preparation. Pamrevlumab will be administered by IV infusion, using an infusion set with a sterile, nonpyrogenic, low-protein-binding in-line filter (0.2-micron pore size).

### 6.1.5. Administration

Study Drug	Dose	Route	Infusion Rate	Schedule
Pamrevlumab	35 mg/kg	IV	Not to exceed 150 cc/hour	Every 2 weeks
DO NOT ADMINISTER PAMREVLUMAB AS AN IV PUSH OR BOLUS INJECTION, OR CONCURRENTLY IN THE IV LINE WITH OTHER AGENTS.				

Subjects who weigh more than 117 kg will receive the maximum allowed dose of 4.1 g. For this study, the overall rate of infusion for the prepared study drug should not exceed 150 cc/hour. Adjustments may be made to further slow the rate of infusion (infusing less than 150 cc/hour) in accordance with the investigator's clinical judgement. Subjects should be carefully monitored for reaction during the first infusion with a physician available as needed. Subjects will remain at the study site for 1 hour after the end of the infusion for clinical observation. The IV access should remain in place and be maintained per site procedures until the end of this post treatment observation period. If a subject has an infusion reaction, the infusion rate may be slowed or temporarily stopped, depending on the severity of symptoms. If a subject experiences an infusion reaction and continues pamrevlumab dosing, a physician must be immediately available during subsequent infusions and observation periods until the subject does not have any infusion reaction for three sequential infusions.

Premedication, such as antihistamines, corticosteroids or nonsteroidal anti-inflammatory drugs (NSAIDs) are not normally administered before infusions of pamrevlumab.

Premedication may be used for subjects who experience infusion reactions at the discretion of the investigator after discussion with the Medical Monitor.

Pamrevlumab will be administered in a hospital or ambulatory setting with adequate facilities for managing medical emergencies for at least three infusions to confirm the subject does not have an infusion reaction. The study site must have trained staff and medications for the treatment of acute reactions, including anaphylaxis, immediately available. There is no specific treatment for a pamrevlumab overdose or infusion reaction. Signs and symptoms should be managed with appropriate standard of care treatment.

FibroGen may consider the use of properly trained home health care staff to administer the pamrevlumab infusions in the future and corresponding study assessments during the conduct of the study, consistent with institutional regulations and policies.

## 7. ASSESSMENT OF EFFICACY AND PHARMACOKINETICS

### 7.1. Study Procedures by Visit

All study procedures and assessments for the main study will be performed in accordance with the Schedule of Assessments presented in [Section 16](#) and in [Appendix 6](#) for the OLE.

For all potential subjects, screening procedures required to determine subject eligibility will be performed within 28 days prior to Day 0 (first infusion of pamrevlumab).

Potential subjects may be re-screened if initial screening procedures lie outside the 28-day screening period prior to planned study entry.

Subject's eligibility for this study will be reviewed and approved by Sponsor's medical monitor prior to subject enrollment.

The following assessments are relevant to the assessment of efficacy: pulmonary function tests (FVC, mean inspiratory flow (MIF), peak expiratory flow), Brooke Upper Extremity Rating Scale, Performance of the Upper Limb, pinch strength, grip strength, cardiac MRI, and muscle MRI. Refer to the Study Reference Manual for details.

Approved windows for performing study assessments are defined in the following sections.

#### 7.1.1. Screening Period (no earlier than Day -28)

Assessments to be conducted during the screening period are presented in [Appendix 1](#).

Screening assessments may be completed over several visits during the screening period. It is recommended that the less invasive screening assessments be performed first upon completion of the signed Informed Consent and/or Assent Form [ICF] (demographics, medical history, blood draws, electrocardiogram [ECG], vital signs (includes body weight and height), physical exam, pulmonary function tests (PFTs), and then followed by the more rigorous screening assessments (i.e., muscle function tests, cardiac MRI).

A cardiac MRI performed within 3 months prior to Day 0 (start of dosing) is acceptable to confirm eligibility based on the LVEF study entry criterion and as baseline cardiac MRI. If an historic MRI is not available, a cardiac MRI must be performed during the Screening Period.

An upper arm muscle MRI is not required to determine subject eligibility at screening, but may be conducted within the screening period (4 weeks prior to Day 0) or anytime up to Week 4 dosing visit (4 weeks after Day 0). The results of this assessment are acceptable as baseline assessment.

Muscle and pulmonary function tests (PFTs) will be performed during the screening period. Muscle function and PFTs will be repeated on Day 0 (start of dosing) or at any time up to and including the Week 2 visit. The results from both time points will be used to establish baseline values.

If the subject cannot perform adequately due to illness (e.g. sinusitis, etc.) then the PFTs should be delayed until the subject can reliably perform the assessment within the 28-day screening window.

In addition, an exploratory blood sample will be drawn for analysis of circulating biomarkers of fibrosis and specific muscle miRNAs (dystromirs) prior to first pamrevlumab infusion.

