#### **7.2.7.2.    Pharmacokinetics**

Plasma concentrations of pamrevlumab will be determined on Day 0 pre-dose and within 1 hour post infusion, then on Days 2, 4, 7, 10, and 14. The Day 14 sample should be on the same day of, but prior to the start of the next infusion of study drug.

Day 2, 4, 7, and 10 PK assessments represent target days following the first dose; however, actual sample collection time of up to  $\pm 1$  day of the target time is acceptable as long as the actual time of dosing and actual time of each sample collection are recorded accurately.

At Weeks 26 and 52, trough pamrevlumab levels (Cmin) will be determined prior to study drug infusion.

PK samples will also be drawn within 60 minutes of infusion completion at Week 52.

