- g. Pulmonary function tests (PFTs): forced vital capacity, forced expiratory volume in 1 second, maximal inspiratory pressure, maximum expiratory pressure, peak expiratory flow rate, peak cough flow. PFTs will be performed during the screening period. PFTs will be repeated on Day 0 (start of dosing) or at any time up to and including the Week 2 visit. The results from both time points will be used to establish baseline values.
- h. See [Appendix 5](#) for pharmacokinetic/human antihuman antibody/connective tissue growth factor and Exploratory Sample collection details.
- i. Baseline muscle MRI may be conducted during the screening period or up to Week 4 dosing visit. Local safety labs are required prior to the MRIs, and must include hematocrit.

## APPENDIX 2. SCHEDULE OF ASSESSMENTS: WEEK 28 THROUGH WEEK 58

Assessment a	Treatment Period (Weeks)													
	28	30	32	34	36	38	40	42	44	46	48	50	52	54,56, 58
Clinical laboratory assessments b,i					X						X			
Vital Signs c	X	X	X	X	X	X	X	X	X	X	X	X	X	X
Weight/Height d					X						X			
Electrocardiogram												X		
Physical Examination e					X						X			
Muscle function tests f					X						X			
Pulmonary function tests g					X						X			
Cardiac MRI i													X	
Muscle MRI i													X	
Specialty labs h														X
Pamrevlumab infusion	X	X	X	X	X	X	X	X	X	X	X	X	X	X
Adverse Events & Concomitant Medications	X	X	X	X	X	X	X	X	X	X	X	X	X	X
PODCI Quality Outcome Questionnaire													X	

Abbreviations: MRI, magnetic resonance imaging; PODCI, Pediatrics Outcomes Data Collection Instrument

- See [Section 7](#) for details on approved windows, assessments and dosing.
- Safety labs: See [Section 7.2.7.1](#). Central labs are required at visits noted in this table.
- Vital signs (pulse, respiration, sitting blood pressure, and temperature) to be collected at every visit, and pre-infusion, within 15 minutes of infusion completion and within 15 minutes of completing the observation period.
- Weight and height (estimated from ulna length) to be measured at screening and approximately every 3 months thereafter.
- Physical exam to include assessment of subject's ventilation use. A complete exam is required at Week 48. Other exams may be disease specific or problem oriented.
- Muscle function tests: Brooke Scale, Performance of Upper Limb, Pinch Strength Test, and Grip Test.

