15. APPENDICES

APPENDIX 1. ANALYSIS VISIT WINDOWS

Table 1: Assessment Windows for PFT

Analysis Visit	Window
Baseline	Value at the visit on or prior to the first dose of study drug Target day=1, window = $[L_0, H_0] = [-, 1]$
Week X	$X = 24*K$, $k=1, 2, \dots, 7$ Target day = $7 * X + 1$ Window = $[L_K, H_K] = [H_{K-1}+1, \text{Target Day}+24*7/2-1]$
Week 192	$[L_8 = H_7+1 = 1261, **]$

** There will be no upper bound; all assessments will be included.

Table 2: Assessment Windows for Muscle Function Tests

Analysis Visit	Window
Baseline	Value at the visit on or prior to the first dose of study drug Target day=1, window = $[L_0, H_0] = [-, 1]$
Week X	$X = 12*K$, $k=1, 2, \dots, 16$ Target day = $7 * X + 1$ Window = $[L_K, H_K] = [H_{K-1}+1, \text{Target Day}+12*7/2-1]$
Week 204	$[L_{17} = H_{16} +1=1387, **]$

** There will be no upper bound; all assessments will be included.

Table 3: Assessment Windows for Cardiac MRI

Analysis Visit	Window
Baseline	Value at the visit on or prior to the first dose of study drug Target day=1, window = $[L_0, H_0] = [-,1]$
Week X	$X = 52*K$, $k=1, 2, 3$ Target day = $7 * X + 1$ Window = $[L_K, H_K] = [H_{K-1}+1, \text{Target Day}+52*7/2-1]$
Week 208	$[L_4 = H_3+1= 1275, **]$

* There will be no upper bound; all assessments will be included.

Table 4: Assessment Windows for Vital Signs

Analysis Visit	Window
Baseline	Baseline are defined as the average of last Screening and Week 0 pre-infusion measurements. Target day=1, window = $[L_0, H_0] = [-,1]$
Week X	$X = 2*K$, $k=1, 2, 3, \dots, 105$ Target day = $7 * X + 1$ Window = $[L_K, H_K] = [H_{K-1}+1, \text{Target Day}+6]$

*The last visit window will not have an upper bound; all assessment will be included.

Table 5: Assessment Windows for Labs Tests

Analysis Visit	Window
Baseline	Value at the visit on or prior to the first dose of study drug Target day=1, window = $[L_0, H_0] = [-,1]$
Week X	$X = 24*K$, $k=1, 2, \dots, 8$ Target day = $7 * X + 1$ Window = $[L_K, H_K] = [H_{K-1}+1, \text{Target Day}+24*7/2-1]$
Week 210	$[L_9 = H_8+1= 1408, **]$

* There will be no upper bound; all assessments will be included.

All scheduled and unscheduled assessments are included in the by-visit summary. If more than two assessments are available in the same window, the last assessment will be used in the by- visit summary.

If any visit is missed, assessments should be performed as soon after the missed visit as feasible. Missed infusions will not be replaced.

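### The repeat lung and muscle function tests that enter the main-study baseline may be done after the first infusion, so part of that baseline may be on-treatment

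*Protocol*

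**What the plan says.** Protocol Section 7.1.1 sets two baseline occasions for the pulmonary function tests and muscle function tests. The first falls in screening: "Muscle and pulmonary function tests (PFTs) will be performed during the screening period". For the second, the tests are to be "repeated on Day 0 (start of dosing) or at any time up to and including the Week 2 visit". It then adds: "The results from both time points will be used to establish baseline values".

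Appendix 1 repeats the rule in footnote f (Brooke, PUL, pinch, grip) and footnote g (FVC and the other lung tests): "PFTs will be repeated on Day 0 (start of dosing) or at any time up to and including the Week 2 visit". The grid itself marks these tests at screening and Day 0; the extension to Week 2 is in the text and footnotes.

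Section 7.1 identifies Day 0 as the day of the first infusion, and Week 2 is the next infusion visit. Neither Section 7.1.1 nor the footnotes say how the two results are combined.

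The supplied SAP covers the open-label extension (OLE). Its Section 5.4.3 refers the main-study baseline to the main-study SAP, which is not among the documents. Its Section 9.2 analyses long-term efficacy from the main-study baseline unless otherwise noted.

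**The concern.** A repeat test can follow one infusion, or two if it is done after the Week 2 infusion, and the protocol still requires it to enter baseline. This is not merely a convention left unsaid, because the protocol states a pre-dose condition where it wants one. For the pharmacokinetic sample it says: "The Day 14 sample should be on the same day of, but prior to the start of the next infusion of study drug". Section 7.1.1 itself places the exploratory blood sample before the first infusion. The test that feeds the primary endpoint has no such condition.

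The trial has one arm and is judged against a fixed value: success requires the lower 95% confidence bound for annual change in percent predicted FVC to lie above -5% (Protocol Sections 9.1 and 9.4.1). No control group would share and cancel a baseline shift. A fall in FVC after the first infusion would lower baseline and make later decline look smaller. An early gain or a learning effect would raise baseline and count against the drug. The PUL, grip, pinch and Brooke endpoints use the same two-test baseline.

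**Working it through.** **The plan's own figure.** Protocol Section 9.1 gives 22 subjects for 80% power, with null -5, mean -2, SD 5 and two-sided 0.05. By the normal approximation, n = (5 × (1.960 + 0.842) / 3)² = 21.8, so 22, with power 80.4%. With the exact one-sample t-test, power at 22 is 76.5%. The baseline point does not depend on this difference; 76.5% is the reference for power below.

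**Infusions before the repeat test.** None if it is done on Day 0 before the infusion; one if done after the Day 0 infusion and before the Week 2 infusion; two if done after the Week 2 infusion.

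**Effect on the annual change.** Let d be the shift in the repeat value relative to its pre-dose value, and p the share of subjects tested after dosing. Assume that the two tests are averaged and the 104-week change is divided by 2. Mean baseline then moves by p × d/2, and the mean annual change by -p × d/4. If the repeat alone were used, the movement would be -p × d/2. The documents give no value for d, p or the combining rule.

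**Illustration with p = 1, averaging, n = 22, SD 5, exact t:**

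| d (points) | Movement in annual change | Operating characteristic |
|---|---|---|
| -1 | +0.25 | success at a true -5: 4.1% (nominal 2.5%) |
| -2 | +0.50 | success at a true -5: 6.5% |
| -3 | +0.75 | success at a true -5: 9.9% |
| -4 | +1.00 | success at a true -5: 14.4% |
| +1 | -0.25 | power at -2: 69.2% (from 76.5%) |
| +2 | -0.50 | power at -2: 60.9% |

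With half the subjects tested after dosing, the mean movement halves.

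**The part that needs no drug effect.** Take a decline of 5 points per year (the null value) to 8 (the median loss in Protocol Section 2.2). A repeat at Week 2 instead of Day 0 comes 14 days later, or 16 with the 2-day visit window. The decline is 5 × 14/365.25 = 0.19 to 8 × 16/365.25 = 0.35 points. Divided by 4, this is 0.05 to 0.09 points per year, in the favourable direction if follow-up time is not re-anchored. It is measured against a repeat on Day 0; the screening test, up to 28 days before Day 0, pulls the other way.

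**The OLE random coefficient model.** SAP Section 9.2.2.1 and Appendix 2 model change = b0 + b1 × time + b2 × baseline, with random intercept and slope. Add s to every subject's baseline. Each post-baseline change falls by s and the covariate rises by s:

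change - s = (b0 - s - b2 × s) + b1 × time + b2 × (baseline + s).

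The slope b1 is unchanged and the intercept absorbs the shift. The estimate at year k, taken at the mean baseline, moves by -s. An MMRM change at the mean baseline also moves by -s. This assumes that only post-baseline records enter the model and that the shift is common to all subjects.

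**The case against.** The strongest reply has four parts.

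- **The missing SAP.** The main-study SAP exists (the Addendum cites version 1.0 of June 25, 2020) and may restrict baseline to pre-dose values. This cannot be checked. If it does, it departs from the protocol's wording and the two need reconciling.
- **Size.** No document reports a shift in FVC within two weeks of a first infusion. The error rates in the table need the same fall in every subject and every repeat done after dosing, although the grid places the repeat on Day 0. This stands: the table shows sensitivity and is not a forecast. The one component based on the documents' own rates, natural decline, is trivial against a 3-point effect and SD 5.
- **Calculation of the endpoint.** The -d/4 rule assumes a simple difference divided by two. No supplied text says that the main study computes annual change this way, and under a random coefficient model like the one supplied a common shift would not reach the slope. This also stands.
- **The OLE rule.** A reader might see a contradiction with SAP Appendix 1, Table 1, where PFT baseline is "Value at the visit on or prior to the first dose of study drug". SAP Section 5.4.3 ties the OLE baseline to the first OLE dose, in subjects already treated for at least 104 weeks. It is a different baseline for a different period, so there is no contradiction; it shows only that the sponsor can write a pre-dose rule.

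None of this removes the protocol's instruction, which admits post-infusion tests and requires their use.

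**Conclusion.** The point holds in a limited form. Under Protocol Section 7.1.1 and Appendix 1 footnotes f and g, part of the main-study baseline for percent predicted FVC and the muscle endpoints may be on-treatment. The direction and size of any bias are unknown. Under averaging and halving, it is d/4 points per year for each d points of shift, times the share of subjects tested after dosing.

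Two stronger readings are not supported. A reader might infer that the primary change starts from an on-treatment value. The screening test is always pre-dose and always part of baseline, so a wholly on-treatment baseline would need a rule such as taking the last or best value, which the documents neither state nor exclude. A reader might also infer that all OLE results inherit the problem. A common shift reaches the year-by-year estimates and the MMRM changes for the affected endpoints, but not the annual slope of the supplied model.

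This is a cheap improvement and does not by itself undermine the primary result.

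**What to change.** **For any subject not yet dosed.** Amend Section 7.1.1 and footnotes f and g so that only pulmonary and muscle function tests completed before the start of the first infusion count toward baseline. Where there is no pre-dose repeat, use the screening test alone. State how two pre-dose results are combined.

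**For subjects already enrolled.** The SAP Addendum, Section 1, says that the study has reached database lock and an interim report is complete. Replacing the specified baseline after open-label results are known would create a new problem. Keep it as primary, report how many repeat tests were done after the first infusion, and add a sensitivity analysis of the primary and muscle endpoints using pre-dose values only.

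**Cost.** Wording, one count and one extra analysis; the Day 0 visit already exists. Subjects without a pre-dose repeat have one baseline test instead of two. With an assumed test-retest SD of 3 points, baseline error variance rises from 9/2 = 4.5 to 9. Annualising divides the extra 4.5 by 4, adding 1.1 to a variance of 25. The standard error rises by √(26.1/25) - 1, about 2%, if this applied to every subject.
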